#### 9.7.1.7 Pharmacokinetic, Pharmacodynamic, Pharmacogenomic, and Other Biomarker Analyses

##### 9.7.1.7.1 PHARMACOKINETIC ANALYSES

All PK analyses will be performed on the PK Analysis Set.

Lenvatinib plasma concentration data, including data from subjects randomized before implementation of Amendment 03, will be summarized using descriptive statistics and plotted as appropriate for each treatment group.

In addition lenvatinib plasma concentration data will be analyzed using a population PK approach to estimate population PK parameters. The analyses will be detailed in a separate analysis plan and reported separately from the CSR.

##### 9.7.1.7.2 PHARMACOKINETIC/PHARMACODYNAMIC ANALYSES

Pharmacokinetic/pharmacodynamic data from subjects randomized before implementation of Amendment 03 will be included in the models.

Lenvatinib exposure parameters (AUC or concentration at the time of the event or cumulative AUC, as appropriate) derived from the population PK analysis will be related to biomarker, safety, and efficacy data and will be modeled using a mechanistically based approach, if possible. For some PK/pharmacodynamic analyses, data from this study will be pooled with data from the RR-DTC arm of the Phase 2 Study E7080-G000-201 (Study 201) and with data from the RR-DTC Phase 3 Study E7080-G000-303 (Study 303).

For efficacy, a tumor growth inhibition model based on longitudinal tumor size measurements of target lesions will be included. The plan is to explore both lenvatinib exposure and/or measured biomarkers (including thyroglobulin [accounting for anti-Tg], TSH, VEGF, Ang-2, sTie-2, FGF23) as predictors and/or correlations with tumor burden changes in the tumor growth inhibition model.

Other analyses will include logistic regression analysis for  $ORR_{24wk}$ , KM plots of PFS data stratified by lenvatinib exposure, and Cox-regression analysis. For the Cox-regression analysis of PFS, adjustment will be made for a subject's baseline characteristics or tumor-related features. In addition to lenvatinib exposure, changes in biomarker concentrations (thyroglobulin and TSH) and/or tumor burden will be related to PFS.

For the exposure-response relationship of safety, the model-based analysis will include the following AEs: hypertension, proteinuria, weight loss, fatigue, nausea, vomiting and

diarrhea. For hypertension, BP data will be analyzed using an indirect-response model. For proteinuria, urine dipstick and/or 24-hour urine data will be analyzed using a longitudinal categorical logistic regression analysis with Markov element. For weight loss, fatigue, nausea, vomiting, and diarrhea, data will be analyzed using a longitudinal categorical logistic regression analysis. For time to treatment discontinuation due to an AE and time to first dose reduction, KM plots stratified by lenvatinib exposure will be prepared.

For the exposure-response relationship for biomarkers, thyroglobulin (accounting for anti-Tg), TSH, VEGF, Ang-2, sTie-2, and FGF23 data will be analyzed using a model-based approach. Direct, indirect, and effect compartment models will be explored.

Population PK and PK/pharmacodynamic analyses will be detailed in a separate analysis plan and reported separately from the CSR.

#### 9.7.1.7.3 BIOMARKER ANALYSIS

The effect of lenvatinib treatment on serum thyroglobulin, TSH, and other exploratory serum biomarkers will be summarized by treatment group. In addition, association between clinical outcomes and baseline biomarker levels, and/or change in levels from baseline will be explored. The analyses may be detailed in the BAP and reported separately.

#### 9.7.1.8 Safety Analyses

All safety analyses will be performed on the Safety Analysis Set. All safety analyses will be summarized separately by treatment group. Adverse events and SAEs, laboratory test results, physical examination findings, vital signs, and echocardiogram results (including LVEF), and their changes from Baseline will be summarized using descriptive statistics. Abnormal values will be flagged. Safety data from subjects randomized before Amendment 03 will be reported in a separate report, and will also be included in the final CSR for this study.

Time to treatment discontinuation due to an AE, number of dose reductions, and time to first dose reduction will be summarized.

##### 9.7.1.8.1 PRIMARY SAFETY ENDPOINT

For the analysis of the primary safety endpoint, the frequency (number and percentage) of TEAEs with CTCAE grade of 3 or higher will be summarized by treatment group (24 mg and 18 mg); the difference in the frequency between the 2 treatment groups will be presented with 95% CI.

##### 9.7.1.8.2 EXTENT OF EXPOSURE

The number of cycles/days on treatment, quantity of study drug administered, and the number of subjects requiring dose reductions, treatment interruption, and treatment discontinuation due to AEs will be summarized.

### 9.7.1.8.3 ADVERSE EVENTS

The AE verbatim descriptions (investigator terms from the CRF) will be classified into standardized medical terminology using the Medical Dictionary for Regulatory Activities (MedDRA). Adverse events will be coded to the MedDRA (Version 16.1 or higher) lower level term closest to the verbatim term. The linked MedDRA preferred term and primary system organ class (SOC) are also captured in the database.

TEAEs will be defined as AEs that emerge during treatment, having been absent pretreatment (at baseline) or those that:

- Reemerges during treatment, having been present at pretreatment (Baseline) but stopped before treatment, or
- Worsens in severity during treatment relative to the pretreatment state, when the AE is continuous.

Only those AEs that are treatment-emergent will be included in summary tables. All AEs, treatment-emergent or otherwise, will be presented in subject data listings.

An overview table, including the incidence of and the number of subjects with TEAEs, SAEs, deaths, and those TEAEs that led to study drug discontinuation, dose modification, or dose interruption will be provided.

The incidence of TEAEs will be summarized by SOC, preferred term, CTCAE grade, and relatedness to study drug. All summaries will be performed by treatment group. Although a MedDRA term may be reported more than once for a subject, that subject will be counted only one time in the incidence count for that MedDRA term with the highest CTCAE grade (in the summary by CTCAE grade) or with the closest relationship to study treatment (in the summary by relatedness to study treatment).

The number (percentage) of subjects with TEAEs will also be summarized by relationship to study drug (Yes [related] and No [not related]).

In addition, the overall proportion of subjects with TEAEs of CTCAE Grade 3 or higher and the overall proportion of subjects with intolerable CTCAE Grade 2 TEAEs that result in dose modification will be analyzed using the same approach for the primary safety endpoint, as sensitivity analyses.

### 9.7.1.8.4 LABORATORY VALUES

Laboratory test results, vital signs and their changes from baseline, and 12-lead ECG results, will be summarized using descriptive statistics. Abnormal values will be flagged.

Laboratory results will be summarized using Système International units, as appropriate. For all quantitative parameters listed in [Section 9.5.1.4.3](#), the actual value and the change from baseline to each postbaseline visit and to the end of treatment (defined as the last on-treatment value) will be summarized by visit and treatment arm using descriptive statistics. Qualitative parameters listed in [Section 9.5.1.4.3](#) will be summarized using

frequencies (number and percentage of subjects), and changes from baseline to each postbaseline visit and to end of treatment will be reported using shift tables. Percentages will be based on the number of subjects with both nonmissing baseline and relevant postbaseline results.

Laboratory parameters will be categorized according to CTCAE v4.0 grades and shifts from baseline CTCAE grades to maximum and the last postbaseline grades will be assessed. The CTCAE Grade 3 and 4 test results will be summarized.

#### 9.7.1.8.5 VITAL SIGNS AND PHYSICAL EXAMINATION FINDINGS

Changes from baseline in vital signs parameters (resting BP, pulse, RR and body temperature, weight) and height will be summarized. See the Schedule of Procedures and Assessments in [Table 7](#).

#### 9.7.1.8.6 ELECTROCARDIOGRAMS

Descriptive statistics for ECG parameters and changes from baseline will be presented by visit, by starting dose, and by dose at the assessment time. Shift tables will present changes from baseline in ECG interpretation (categorized as normal; abnormal, not clinically significant; and abnormal, clinically significant) by visit.

In addition, the number (percentage) of subjects with at least 1 postbaseline abnormal ECG result in QTc Bazett and QTc Fridericia during the treatment period will be summarized. Clinically abnormal ECG results in QTc Bazett and QTc Fridericia will be categorized as follows:

Absolute QTc interval prolongation:

- QTc interval >450 ms
- QTc interval >480 ms
- QTc interval >500 ms

Change from baseline in QTc interval:

- QTC interval increases from baseline >30 ms
- QTC interval increases from baseline >60 ms

#### 9.7.1.8.7 OTHER SAFETY ANALYSES

MUGA scans and echocardiograms will be assessed locally. Descriptive summary statistics for LVEF changes from baseline will be calculated and summarized.

#### 9.7.1.8.8 HEALTH-RELATED QUALITY OF LIFE ANALYSES

Descriptive statistics of the derived functional/symptom scales according to the scoring manual and global health status scores will be summarized at each time point by starting dose. A separate prespecified HRQoL analysis following FDA and EMA patient-reported

outcomes Guidelines will be performed and detailed in a separate SAP and a separate HRQoL report.

### 9.7.2 Determination of Sample Size

Sample size determination is based on the number of subjects required to detect noninferiority of the primary efficacy endpoint, ORR24wk, comparing the 18-mg arm to the 24-mg arm. Based on the data from Study 303, the ORR24wk for the lenvatinib 24-mg arm was 54.4% (142 responders, N=261) and 0.8 % for the placebo arm (1 responder, N=131) and the lower 95% CI of the OR for lenvatinib 24 mg vs placebo was 21.4. Assuming a 70% retention of the effect of lenvatinib 24 mg versus placebo, the noninferiority margin on the OR scale is estimated to be 0.40 (ie, Ha: OR [18 mg/24 mg] >0.4).

A sample size of 152 subjects (76 per arm) will provide a statistical power of 80% to declare noninferiority, assuming a 1-sided alpha of 0.025, an ORR24wk of 54.4% for lenvatinib 24 mg and a true OR of 1, with a noninferiority margin of 0.4.

For the primary safety endpoint, based on the data from Study 303, where 70.5% of subjects in the lenvatinib 24-mg arm had a TEAE of CTCAE Grade 3 or higher during the first 24 weeks, the sample size of 152 subjects will provide a precision for the observed differences between the arms with half widths of the 95% CI of about 15%.

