### **Sample Size Rationale**

As of Amendment 03, the sample size determination is based on the required number of subjects to detect noninferiority of the primary efficacy endpoint  $ORR_{24wk}$ , comparing the 18-mg arm to the 24-mg arm. Assuming a 70% retention of the effect of lenvatinib 24 mg versus placebo in Study 303, the noninferiority margin on the odds ratio (OR) scale is estimated to be 0.40 (ie,  $H_a$ : OR [18 mg/24 mg] >0.4). A sample size of 152 subjects (76 per arm) will provide a statistical power of 80% to declare noninferiority, assuming a 1-sided alpha of 0.025, an  $ORR_{24wk}$  of 54.4% for lenvatinib 24 mg, and a true OR of 1 with a noninferiority margin of 0.4. The sample size of 152 subjects will also provide a precision for the observed differences between the arms with half-widths of the 95% CI of about 15%.

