The revised study design of Protocol Amendment 03 is guided by results of new modeling and simulation data that indicate that the starting dose of 14 mg is considered highly unlikely to achieve efficacy comparable to the approved starting dose of 24 mg, whereas a starting dose of 20 mg is not sufficiently distinct from 24 mg to achieve improved safety. Therefore, an 18-mg starting dose was selected as the comparator. More information appears in Section 7.3.

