**Table 1 Simulated Objective Response Rate at 24 Weeks**

Dosing Regimen	ORR (%)
	24 weeks
24 mg without up-titration	50.0
18 mg without up-titration	41.5
14 mg with up-titration	41.7
20 mg without up-titration	43.5

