**Table 1 Simulated Objective Response Rate at 24 Weeks**

Dosing Regimen	ORR (%)
	24 weeks
14 mg without up-titration	30.2

Dose levels in italics were those in the initial study design.

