## 8 STUDY OBJECTIVES

### 8.1 Primary Objective

- To determine whether a starting dose of lenvatinib 18 mg once daily (QD) will provide comparable efficacy (based on ORR24wk) with an improved safety profile compared to 24 mg QD (based on treatment-emergent adverse events [TEAEs] of Grade 3 or higher in the first 24 weeks after randomization).

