4 DETERMINATION OF SAMPLE SIZE

Sample size determination was based on the number of subjects required to detect noninferiority of the primary efficacy endpoint, ORR_{24wk} , comparing the 18 mg arm to the 24 mg arm. Based on the data from Study 303, the ORR_{24wk} for the lenvatinib 24 mg arm was 54.4% (142 responders, N=261) and 0.8 % for the placebo arm (1 responder, N=131) and the lower 95% CI of the Odds Ratio for lenvatinib 24 mg vs placebo was 21.4. Assuming a 70% retention of the effect of lenvatinib 24 mg versus placebo, the noninferiority margin on the Odds Ratio scale was estimated to be 0.40 (i.e, H_a : Odds Ratio [18 mg/24 mg] >0.4).

A sample size of 152 subjects (76 per arm) would provide a statistical power of 80% to declare noninferiority, assuming a 1-sided alpha of 0.025, an ORR_{24wk} of 54.4% for lenvatinib 24 mg and a true Odds Ratio of 1, with a noninferiority margin of 0.4.

For the primary safety endpoint, based on data from Study 303, where 70.5% of subjects in the lenvatinib 24 mg arm had a TEAE of Common Terminology Criteria for Adverse Events (CTCAE) Grade 3 or higher during the first 24 weeks, the sample size of 152 subjects provides a precision for the observed differences between the arms with half-widths of the 95% CI of about 15%.

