5.4 Efficacy Analyses

5.4.1 Primary Efficacy Analyses

The noninferiority analysis of ORR_{24wk} between lenvatinib starting doses of 24 mg and 18 mg will be performed at the 1-sided alpha of 0.025, based on the calculated odds ratio of ORR_{24wk} response (18 mg vs 24 mg) along with its 95% confidence interval (CI) using the Cochran-Mantel-Haenszel (CMH) method, stratified by the randomization stratification factors. The test will be performed per the 95% CI using the noninferiority margin of 0.4. Noninferiority will be declared if the lower limit of the 95% CI for the odds ratio is greater than 0.4.

The point estimate of ORR_{24w} for each group will be summarized with the corresponding 95% CI using asymptotic normal approximation. Treatment difference (18 mg minus 24 mg) will also be estimated with its 95% CI using asymptotic normal approximation.

SENSITIVITY ANALYSIS

A sensitivity analysis will be performed for overall ORR using the same methods as used for ORR_{24wk} .

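### Does the 0.40 odds-ratio margin let through the 14-mg regimen that the protocol rejected?

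*Protocol*

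**What the plan says.** The primary objective in Protocol 8.1 is "To determine whether a starting dose of lenvatinib 18 mg once daily (QD) will provide comparable efficacy", judged on the 24-week objective response rate (ORR), with a better safety profile. Protocol 9.7.2 takes the Study 303 results (142/261 responders on 24 mg, 1/131 on placebo, lower 95% limit of the odds ratio 21.4), assumes 70% retention, and concludes that "the noninferiority margin on the OR scale is estimated to be 0.40". The synopsis and SAP 4 repeat this ("the noninferiority margin on the Odds Ratio scale was estimated to be 0.40"). SAP 5.4.1 gives the decision rule: "Noninferiority will be declared if the lower limit of the 95% CI for the odds ratio is greater than 0.4". It also reports each arm's response rate, and the difference between arms, with 95% confidence intervals.

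The dose rationale is separate. Protocol 7.2 says that a 14-mg starting dose "is considered highly unlikely to achieve efficacy comparable to the approved starting dose of 24 mg". Section 7.3 bases the change of dose on simulations. In Table 1 the row "24 mg without up-titration" shows 50.0%, the row "14 mg without up-titration" shows 30.2%, and 18 mg shows 41.5%. Beside these tables the text says only that 14-mg efficacy might suffer. Section 9.2 goes further: it says the simulated median 14-mg rate would fall by over half relative to 24 mg, and for that reason calls the dose unacceptable on efficacy.

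**The concern.** The protocol uses one idea, comparable efficacy, for two purposes. As a reason to drop 14 mg, a simulated fall from 50.0% to 30.2% counts as not comparable. As the target of the primary test, any odds ratio above 0.40 counts as noninferior, and that fall has an odds ratio of 0.433. On Table 1's figures the margin therefore tolerates slightly more loss than the loss for which a dose was rejected. No section relates the margin to Table 1 or expresses it as response rates.

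At stake is how a narrow success would be read. With 41/76 responders on 24 mg and 36/76 or 37/76 on 18 mg, the rule is met, yet the confidence interval still contains 0.433. A reader could ask whether comparable efficacy had been shown by the protocol's own standard. Section 9.2 adds to the doubt, because a fall of more than half would lie on the other side of the margin.

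**Working it through.** **The plan's own figures.** Inputs are from Protocol 9.7.2.

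- Study 303 odds ratio: (142 × 130)/(119 × 1) = 155.1. The lower 95% limit on the log scale is 21.36 (stated 21.4).
- Margin at 70% retention on the log scale: 21.4^-(1-0.70) = 0.399, which rounds to 0.40.
- Sample size per arm at p = 0.544 and true odds ratio 1: (1.96 + 0.8416)² × [2/(0.544 × 0.456)] / (ln 0.4)² = 75.4, so 76.
- Power at 76 per arm: SE = √[2/(0.544 × 0.456 × 76)] = 0.326, and Φ(0.916/0.326 - 1.96) = 80.3%. Exact enumeration of the unstratified rule gives 80.6%.

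The margin, sample size and power all reproduce.

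**Where the simulated doses fall** (Table 1, against 50.0% on 24 mg, where the odds are 1):

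- 14 mg without up-titration: 0.302/0.698 = 0.433. Relative fall (50.0 - 30.2)/50.0 = 39.6%.
- 18 mg: 0.415/0.585 = 0.709.
- The margin as a rate: 0.4/1.4 = 28.6% when 24 mg is 50.0% (a 42.9% fall), and 32.3% when 24 mg is 54.4% (a 40.6% fall).
- The Section 9.2 description: a fall of exactly half, to 25.0%, has odds ratio 0.333, so a larger fall lies below that and outside the margin.

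**What the rule does to such a dose.** Passing needs an observed odds ratio of at least about 0.76, since exp(ln 0.4 + 1.96 × 0.326) = 0.757. With 76 per arm, the chance of declaring noninferiority is:

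- 4.2% at 30.2% vs 50.0% (exact and approximate);
- 4.2% (approximate) to 4.4% (exact) at odds ratio 0.433 with a 24-mg rate of 54.4%;
- 0.6% (exact) if the rate is halved, 25.0% vs 50.0%.

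**The narrow-success zone.** With 41/76 on 24 mg:

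- 36/76 on 18 mg: odds ratio 0.768, lower limit 0.406;
- 37/76: 0.810, lower limit 0.428;
- 38/76: 0.854, lower limit 0.452.

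The chance of a lower limit between 0.40 and 0.433 is about 7-9% at true odds ratio 1, and 9-12% at 0.709. The ranges span the normal approximation, exact enumeration and a stratified simulation. The stratum sizes in that simulation are assumed (30/30/20/20%), because the documents give none.

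**The price of a 0.433 threshold** (24-mg rate 54.4%, 76 per arm, normal approximation):

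| True odds ratio | Power, limit > 0.40 | Power, limit > 0.433 |
|---|---|---|
| 1 | 80% | 73% |
| 0.85 | 64% | 55% |
| 0.709 | 42% | 33% |

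Restoring 80% at odds ratio 1 would take 91 per arm (182 in total).

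**The case for a change.** The strongest case for a change is that the sponsor redesigned the trial on these simulations, so they cannot be set aside as mere modelling when the margin is discussed. The comparison within Table 1 is like for like. If the true 18-mg odds ratio were Table 1's 0.709, 22-28% of noninferiority declarations would leave 0.433 inside the interval. An interpretive rule for that zone would need no new subjects.

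The arithmetic stands; the inference does not follow. Table 1 predicts an expected effect and was used to decide which dose deserved an arm. The margin is the largest true loss the trial undertakes to exclude, taken from Study 303. A dose expected to fail the test about 96% of the time is reasonably left out without its predicted odds ratio becoming the margin. The one section that calls 14 mg unacceptable ties that verdict to a fall of more than half, which 0.40 already excludes.

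The gap is also fragile. At a 50.0% control rate, 30.2% and 28.6% differ by 1.6 percentage points, and a simulated 24-mg rate of 52.0% would bring the odds ratio to 0.432665/(0.52/0.48) = 0.399. The simulated 24-mg rate is already 4.4 points below the 54.4% observed in Study 303.

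The mismatch between Section 9.2 and Table 1 is real. Section 9.2 refers to a median and Table 1 names no statistic, so they may report different quantities. Reconciling them would tidy the record, but no analysis uses either figure.

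**Conclusion.** No change to the plan follows. The 0.40 margin comes correctly from its disclosed basis, the sample size delivers the stated power under the stated assumptions, and the risk of passing a dose with the simulated 14-mg effect is about 4%. To say that the margin admits that regimen overstates the position: the simulated point value lies just inside the region, but the trial would very probably not pass such a dose.

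A second threshold at 0.433 is the only remedy that could alter a conclusion. It would make a simulated value without uncertainty the test of the primary objective, and would create a result that is noninferior yet not comparable. It would cost about 7 points of power at odds ratio 1 and 9 points at 0.709. That is a trade-off on which reasonable statisticians differ, and the plan's choice is fair. A narrow success will be visible anyway, because SAP 5.4.1 reports the odds ratio, both rates and their difference with confidence intervals.

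This rests on 76 per arm, a 24-mg rate near 50-54.4%, and Table 1 taken at face value. If Section 9.2's larger fall is the right description, the concern disappears altogether.

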### 9.7.3 Interim Analysis

No interim analysis is planned for this study.

### 9.7.4 Other Statistical/Analytical Issues

Not applicable.

### 9.7.5 Procedure for Revising the Statistical Analysis Plan

If the SAP needs to be revised after the study starts, the sponsor will determine how the revision impacts the study and how the revision should be implemented. The details of the revision will be documented and described in the CSR.

---

## **11 PROCEDURES AND INSTRUCTIONS (ADMINISTRATIVE PROCEDURES)**

### **11.1 Changes to the Protocol**

Any change to the protocol requires a written protocol amendment or administrative change that must be approved by the sponsor before implementation. Amendments specifically affecting the safety of subjects, the scope of the investigation, or the scientific quality of the study require submission to health or regulatory authorities as well as additional approval by the applicable IRBs/IECs. These requirements should in no way prevent any immediate action from being taken by the investigator, or by the sponsor, in the interest of preserving the safety of all subjects included in the study. If the investigator determines that an immediate change to or deviation from the protocol is necessary for safety reasons to eliminate an immediate hazard to the subjects, the sponsor's medical monitor and the IRB/IEC for the site must be notified immediately. The sponsor must notify the health or regulatory authority as required per local regulations.

Protocol amendments that affect only administrative aspects of the study may not require submission to health or regulatory authority or the IRB/IEC, but the health or regulatory authority and IRB/IEC (or if regionally required, the head of the medical institution) should be kept informed of such changes as required by local regulations. In these cases, the sponsor may be required to send a letter to the IRB/IEC and the Competent Authorities (or, if regionally required, the head of the medical institution) detailing such changes.

